#### 6.7.1.1. Combining of PEs / Episodes

A minimum of 2 weeks (14 days) must occur between the end date of an earlier PE and the start date of the next PE for the PEs to be considered separate events. Any exacerbations that occur less than 2 weeks from the end date of the previous exacerbation will be considered the same exacerbation and the following rules will be applied:

- the maximum severity between the two will be applied for the combined event,
- the start date of the earlier event will be used as start date for the combined event,
- the end date of the latest event will be used as end date for the combined event,
- the duration of the combined event will be calculated as end date of the combined PE start date of the combined PE + 1,
- the time at risk of combined events will be adjusted by the duration of the start and end date of the combined event as detailed in the previous bullet
- the question "Does this Pulmonary Exacerbation meet the criteria of a Serious Adverse Event?" will show "Yes" if at least one of the combined events reported "Yes"
- symptoms will be uniquely combined, e.g., if "Increased cough" was reported for both individual events, the combined event will have "Increased cough" reported once, otherwise reported symptoms will be concatenated,
- antibiotics use for the individual events will be reported for the combined event as recorded without any modification.

Note: If two or more PEs were combined into a single exacerbation, the single exacerbation will be analyzed.

#### 6.7.1.2. Annualized Rate of PEs

For the primary analysis, the response variable is the number of PEs the participant experiences up to Week 52, with the time at risk of experiencing a PE included as offset in the model.

PEs with a start date that occurs after a participant's discontinuation from IP while remaining in the study for follow-up will be managed according to the Estimand. The time at risk will be adjusted, too (see Table 5).

For descriptive summaries, the crude Annualized Rate of PEs is calculated as:

Annualized Rate of PEs = 
$$\frac{Number\ of\ PEs}{Time\ at\ Risk} * 365.25,$$

where number of PEs and Time at Risk is following the definitions described in Table 5.

CONFIDENTIAL Page 39 of 139

#### 6.7.1.3. Duration of PEs

The duration of PEs (days) will be calculated as

Duration PE (days) = end date of PE - start date of PE + 1.

#### 6.7.1.4. Days Hospitalized for Adjudicated PEs per Person-Year

Hospitalization for adjudicated PEs will be identified through the CRF "Hospitalization visits log" and the reason for hospitalization given as "Indication under study". The recorded admission and discharge dates will be used to calculate participants number of days hospitalized, e.g.,

$$duration(days) = date\ discharge-admission\ date+1.$$

For missing admission or discharge dates, the duration of hospitalization will not be calculated.

The number of days hospitalized due to adjudicated PEs per person-year is calculated as total number of days hospitalized due to indication under study by the total time on treatment:

$$(days\ hospitalized\ for\ indication\ under\ study\ per\ person\_year)_{trt} \\ = \frac{\sum (days\ hospitalized\ for\ indication\ under\ study)_{i,trt}}{\sum time\_on\_treatment_{i,trt}(years)},$$

where i describes the participant of  $trt \in \{\text{brensocatib 10mg, brensocatib 25mg or placebo}\}$ . The total time on treatment in days will be calculated for each treatment (trt) by pooling all patients time on treatment in years together.

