# 2.3. Exploratory Objectives and Endpoints

The exploratory objectives and endpoints are presented in Table 3.

**Table 3:** Exploratory Objectives and Endpoints

Objective		Endpoint		
1.	To evaluate the effect of brensocatib compared with placebo on daily symptoms, as assessed by the average daily BEST score over the 52-week treatment period	Average daily change from Baseline in BEST score over the 52-week treatment period		
2.	To evaluate the effect of brensocatib compared with placebo on the average duration of PEs over the 52-week treatment period	Duration of adjudicated PEs over the 52-week treatment period		
3.	To evaluate the effect of brensocatib compared with placebo on the number of days of hospitalization due to PEs over the 52-week treatment period	Days hospitalized due to adjudicated PEs per patient year over the 52-week treatment period		
4.	To evaluate the effect of brensocatib compared with placebo on the number of days of absence from work (or number of days of school absence in case the subject is of school age) due to PEs over the 52-week treatment period	Days of absence from work/school due to adjudicated PEs per patient year over the 52-week treatment period		
5.	To evaluate the effect of brensocatib compared with placebo on lung function, as measured by change in pulmonary function parameters including prebronchodilator and postbronchodilator FEV 1 , FVC, PEFR, ppFEV 1 , and FEF(25-75%) over the 52-week treatment period	Change from Baseline in prebronchodilator and postbronchodilator FEV 1 , FVC, PEFR, ppFEV 1 , and FEF(25-75%) at Weeks 16, 28, 40, 52, and over 52 weeks		
6.	To evaluate the effect of brensocatib compared with placebo on health care resource utilization (outpatient visits, ER visits, hospitalization for any reason) over the 52-week treatment period	Outpatient visits, ER visits, and hospitalizations for any reason		
7.	To evaluate the effect of brensocatib compared with placebo on quality of life, as assessed by the age-appropriate QOL-PCD domain scores over the 52-week treatment period in adolescent subjects (≥12 to <18 years of age) with PCD	Change in QOL-PCD domain scores from Baseline to Weeks 16, 28, 40, 52, and Over 52 Weeks in adolescent subjects (≥12 to <18 years of age) with PCD		
8.	To evaluate the effect of brensocatib compared with placebo on quality of life, as	Change from Baseline in EQ-5D-5L score from Baseline to Week 52		

Objective	Endpoint

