# 3.2. Data Monitoring Committee and Steering Committee

An independent, external DMC will be set up to review all AEs and SAEs to ensure the safety of subjects enrolled into this study. The DMC members will review the data in a semi-blinded or unblinded manner at predetermined intervals. If significant safety issues arise in between scheduled meetings, ad hoc meetings will be scheduled to review those data. Further details of the DMC will be provided separately in the DMC Charter.

The primary endpoint parameter of this study is PE. An independent adjudication committee (AC) composed of pulmonary physicians will adjudicate all reported PE events to determine if they fulfill the protocol definition. Adjudication outcomes will be used in creation of analysis datasets. Details of the AC will be provided separately in the AC charter.

In addition, an independent Steering Committee will be established to provide study oversight including but not limited to the medical, scientific, operational, safety, and external communication of the study. Details of the Steering Committee will be provided separately in the Steering Committee Charter.

<sup>bAdolescents = male or female participants, ≥12 years to <18 years of age at Screening

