### 6.7. Definitions and Derivations of Efficacy Variables

### 6.7.1. Pulmonary Exacerbations

Only exacerbation events that meet the protocol definition of PE diagnosis confirmed by an independent adjudication committee will be included into the analysis (refer to Section 10.4.6.1.1 of the CSP for further details and the Clinical Endpoint Committee [CEC] Charter).

The calculation of the time at risk as well the inclusion of data into the analysis depends on the underlying Estimand. Refer to Table 5 for further details. In general, participants' time at risk will be the time on study excluding the time during exacerbations.

Table 5: PEs to be included into the analysis and time at risk based on Estimand

Estimand	PEs included in	
Name	the analysis	Time at risk
On-Study	All observed PEs	Date of Week 52 visit / early study
(Primary)	up to Week 52 who	discontinuation  – date of randomization + 1 minus
	meet the protocol	the sum of number of days the participant
	defined criteria of	experiences exacerbation events that meet the
	PE diagnosis	protocol definition of PE diagnosis (end date of the
		PE – start date of the $PE$ + 1). Refer to
		Section 6.7.1.1 for further instructions in case of
		combined PEs.
On-Treatment	All observed PEs	Date of last IP intake / date of first ICE onset –
and On-IP	up to end of IP /	date of first IP intake + 1 minus the sum of number
(Supplementary)	first ICE onset who	of days the participant experiences exacerbation
	meet the protocol	events that meet the protocol definition of PE
	defined criteria of	diagnosis prior to the first ICE (end date of the PE
	PE diagnosis	– start date of the PE + 1). Refer to Section 6.7.1.1
		for further instructions in case of combined PEs.

Rules defined above will not be applied to the analysis of PEs as AEs, e.g., not fulfilling protocol-defined criteria (see Section 7.1 of the CSP).

If a PE is ongoing at EOS, the PE end date will be EOS date, given query for resolution failed. If the PE end date is longer / after the EOS date, then the PE end date will be set to the

CONFIDENTIAL Page 38 of 139

-

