# 6.7.1.5. Days of Absence from Work/School Related to Adjudicated PEs per Patient Year Over the 52 Week Treatment period

To get the number of days absent from work/school the CRF "Missed work/school YN" will be used. Data will only be gathered if both questions "Is the subject currently working or attending school?" and "Has the subject missed any days of work/school since the last visit due to reasons related to bronchiectasis symptoms?" are answered with "Yes".

Missed days of work/school will be identified through the CRF "Missed work/school log". The recorded number of days in the CRF field "How many days?" will be used. The number of days absent from work/school will be linked to the adjudication outcome. Days of absence will be summarized only.

The number of days missed work/school due to adjudicated PEs per year is calculated as total number of days missed by the total time on treatment:

$$(\textit{days missed per person\_year})_{trt} = \frac{\sum (\textit{days missed})_{i,trt}}{\sum \textit{time\_on\_treatment}_{i,trt}(\textit{years})},$$

where i describes the participant of  $trt \in \{\text{brensocatib 10mg, brensocatib 25mg or placebo}\}$ . The total time on treatment in days will be calculated for each treatment (trt) by pooling all patients time on treatment in years together.

CONFIDENTIAL Page 40 of 139

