**Table 8: Exploratory Endpoints** 

Variable	Population Level Summary	Estimand Name	Treatment Regimen	ICEs/ Strategy	Section
Average Daily Change from Baseline in Bronchiectasis Exacerbation and Symptom Tool (BEST) score Over the 52-Week Treatment Period	Mean Difference	On-Study	Assignment to IP regardless of discontinuation or modifications to standard of care	Early discontinuation from randomized IP / Treatment Policy Modification to standard of care / Treatment Policy	8.5.1
Duration of exacerbation events that meet the protocol definition of PE diagnosis Over the 52- Week Treatment Period	Mean Difference	On-Study	Assignment to IP regardless of discontinuation or modifications to standard of care	Early discontinuation from randomized IP / Treatment Policy Modification to standard of care / Treatment Policy	8.5.2
Days Hospitalized for Adjudicated PEs per patient year Over the 52-Week Treatment Period	Mean Annualized Rate	On-IP	Randomized IP regardless of modifications to standard of care	Early discontinuation from randomized IP / While On-Treatment	8.5.3
Days of Absence from Work/School Related to Adjudicated PEs per Patient Year Over the 52-Week Treatment Period	Mean Annualized Rate	On-IP	Randomized IP regardless of modifications to standard of care	Early discontinuation from randomized IP / While On-Treatment	8.5.4

CONFIDENTIAL Page 65 of 139

Change from Baseline in prebronchodilator and postbronchodilator FEV 1 , forced vital capacity (FVC), peak expiratory flow rate (PEFR), percent predicted forced expiratory flow in 1 second (ppFEV 1 ) and forced expiratory flow between 25% and 75% of forced vital capacity (FEF [25-75%] ) at Weeks 16, 28, 40, and 52	Mean Difference	On-Study	Assignment to IP regardless of discontinuation or modifications to standard of care	Early discontinuation from randomized IP / Treatment Policy Modification to standard of care / Treatment Policy	8.5.5
Outpatient Visits, emergency room (ER) visits, and hospitalizations for any reason	Mean Annualized Rate	On-IP	Randomized IP regardless of modifications to standard of care	Early discontinuation from randomized IP / While On-Treatment	8.5.6

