## 8.5.3. Days Hospitalized for Adjudicated PEs per Person-Year Over the 52 Week Treatment Period

The number of days hospitalized for adjudicated PEs per patient year will be presented and will utilize the ITT Analysis Set (see Section 5.2). The derivation of the endpoint is detailed in Section 6.7.1.4.

The number and percentage of participants and the number of hospitalizations, including the duration of hospitalization, the person-time (follow-up time) and the number of days hospitalized per person-year will be summarized descriptively by treatment group.

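### SAP 6.7.1.4 sums all hospital days logged under the reason Indication under study with no link to the adjudication result, so as written it does not measure the exploratory endpoint of hospital days for adjudicated PEs

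*SAP*

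**What the plan says.** Three places define the endpoint in terms of adjudicated events:

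- Protocol 2.3, Table 3: "Days hospitalized due to adjudicated PEs per patient year over the 52-week treatment period".
- SAP Table 8: "Days Hospitalized for Adjudicated PEs per patient year Over the 52-Week Treatment Period", assigned to the On-IP estimand.
- SAP 8.5.3: "The number of days hospitalized for adjudicated PEs per patient year will be presented and will utilize the ITT Analysis Set". This section refers back to 6.7.1.4 for the derivation.

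SAP 6.7.1.4 carries the same label in its title but works differently. It selects stays from the hospitalization log by the recorded reason, *Indication under study*, and takes discharge date minus admission date plus one as the length of stay. It then states: "The number of days hospitalized due to adjudicated PEs per person-year is calculated as total number of days hospitalized due to indication under study", over total time on treatment. The displayed formula repeats the disease reason in its numerator.

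The next section, SAP 6.7.1.5, treats work and school absence differently: "The number of days absent from work/school will be linked to the adjudication outcome".

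**The concern.** A hospital stay for bronchiectasis and a hospital stay for a confirmed PE are different things under the plan's own definitions. A programmer who follows 6.7.1.4 to the letter would produce the first and title the table as the second.

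What is at stake is the meaning of one descriptive table. Its title would tell readers that the hospital days had passed independent adjudication, when nothing in the stated rule makes that so.

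**Working it through.** There is no figure in the plan to reproduce. The check is a comparison of texts, followed by algebra on what the gap could do.

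**1. Does any step bring in adjudication?** The 6.7.1.4 inputs are the log, the recorded reason, the admission and discharge dates, and time on treatment. The adjudication outcome is not among them, and no key or date rule is given for joining a stay to a PE.

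**2. Can the two quantities differ?** Yes.
- Protocol 7.1 requires at least three listed symptoms for at least 48 hours and a physician's decision to prescribe systemic antibiotics. An admission for bronchiectasis can fall short of that.
- Under Protocol 3.2 the adjudication committee "will adjudicate all reported PE events to determine if they fulfill the protocol definition", so reported and confirmed PEs can differ.
- SAP 8.2.5 plans a further analysis of exacerbations the committee designates as clinically relevant. The SAP therefore foresees events outside the confirmed set.

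**3. Is the change declared?** SAP Section 1 says differences from the protocol are discussed in Section 13. That section lists several changes to the Protocol 2.3 endpoints, and this is not one of them.

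**4. What could the gap do to the rate?** Within an arm, let
- A = days logged with the disease reason and belonging to a confirmed PE,
- B = days logged with that reason but not belonging to a confirmed PE,
- C = days belonging to a confirmed PE but logged under another reason.

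The rule as written counts A + B. The endpoint as named is A + C. The denominator is the same, so

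rate as written / rate as named = (A + B) / (A + C) = (1 − g) / (1 − f),

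where f = B/(A + B) and g = C/(A + C).

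The documents give neither f nor g. The values below are assumptions that show the range only:

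| f | g | ratio |
|---|---|---|
| 0.10 | 0 | 1/0.90 = 1.11 |
| 0.20 | 0 | 1/0.80 = 1.25 |
| 0.30 | 0 | 1/0.70 = 1.43 |
| 0.10 | 0.10 | 0.90/0.90 = 1.00 |
| 0 | 0.10 | 0.90/1 = 0.90 |

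The ratio can fall on either side of 1, and nothing in the documents says which. Nor do they say whether f and g would differ between arms.

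**The case against.** The best defence is that 6.7.1.4 sits under SAP 6.7.1, which opens with a general restriction: "Only exacerbation events that meet the protocol definition of PE diagnosis confirmed by an independent adjudication committee will be included into the analysis". The title and first sentence of 6.7.1.4 also speak of adjudicated PEs. On that reading, the log and the reason only name the data source within a scope already limited to confirmed events. The defence can add that the formula in 6.7.1.5 has no adjudication term either, although its text requires the link, so silence in a formula proves little.

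Part of this stands. It shows that the intent was probably to use adjudicated events, and that the gap may be a missing step rather than a deliberate change. It does not repair the derivation. The general sentence governs PE events and does not say how a hospital stay is attached to one. In 6.7.1.5 the text supplies the link that the formula lacks. In 6.7.1.4 both text and formula state the disease reason.

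A reader might also infer four stronger things that the documents do not support:

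- *That stays after study drug ends are counted and inflate the rate where early stopping is more common.* Table 8 assigns On-IP with a While On-Treatment strategy, and SAP 6.6 says data after early discontinuation follow the estimand's strategy. The cut-off is already implied.
- *That the rate is overstated by some 11–25%.* That range is only the second and first rows of assumed f above with g = 0. No source supports those shares.
- *That disagreement with the severe-PE results would show an error.* Severe PEs include events treated with IV antibiotics without admission (SAP 6.7.4), count events rather than days, and use On-Study as the main estimand (SAP Table 2). The two would differ even after a correction.
- *That the investigator's opinion replaces the committee's, or that rejected events will be counted.* The SAP does not say who records the reason. The CRF and the adjudication charter are not among the documents, so whether log records already carry a PE identifier is unknown.

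**Conclusion.** The point holds as a mismatch between a named endpoint and its only operational derivation. Followed as written, SAP 6.7.1.4 yields hospital days for the disease, not for adjudicated PEs, and the SAP does not declare this as a change.

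The conclusion rests on the text alone and needs no assumed rate. The size and direction of the resulting error cannot be determined from the documents.

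The consequence is small. This is an exploratory endpoint, summarized descriptively, with no model or test and no place among the 12 hypotheses in SAP 6.3. Primary and secondary conclusions and type I error control are unaffected. It is a correction worth making because it is cheap and because the table title would otherwise be inaccurate.

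**What to change.** In SAP 6.7.1.4, state that a stay counts only if it carries the reason *Indication under study* **and** is linked to an adjudication-confirmed PE, by PE identifier if one exists or otherwise by date overlap. Change the numerator of the formula to match.

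Keep the reason filter. Under SAP 6.7.1.1, PEs less than 14 days apart are merged, so a combined window can include days between episodes. Overlap alone would then bring in unrelated admissions. The filter leaves out any confirmed-PE stay logged under another reason (C above); a listing of such stays would show whether this matters.

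For clarity, restate that only days up to last IP intake count, as the On-IP estimand already implies.

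If disease-related hospital days are what is wanted, rename the endpoint and list the change in Section 13 instead.

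One knock-on needs care. SAP 6.7.5.8 borrows 6.7.1.4 for hospitalizations that SAP 8.5.6 reports regardless of reason. Neither the present filter nor the corrected one fits that use, so 6.7.5.8 should state its own selection.

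The cost is a few sentences in the SAP and a merge of existing datasets. No new data collection is needed if date overlap is used.

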## 6.6. Reporting of Data After Early Discontinuation of IP

All participants who discontinued IP early are encouraged to stay in the study for continued assessments following the same study procedures until the EOS. Reasons for early IP discontinuation will be recorded. If a participant withdraws consent from continued monitoring, the EOS visit will be completed.

The purposes for collecting these data are to permit full efficacy data ascertainment per the ITT principle in accordance with the On-Study estimand and to allow continual monitoring of participant safety for the 4-week follow-up period after IP discontinuation.

Reporting rules for data collected after early discontinuation of IP are outlined for each data type (efficacy, safety, pharmacokinetic, pharmacodynamic, etc.) per the corresponding estimand, specifically the ICE handling strategy.

Safety data that are excluded from treatment emergent period, i.e., data collected after the 4-week follow-up post early discontinuation of IP, will be reported separately and will include basic summaries of:

- AE, SAEs and AESIs, (non-treatment emergent)
- Laboratory
- Concomitant medication.

Other collected safety data will be listed.

CONFIDENTIAL Page 37 of 139

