# 8.5.4. Days of Absence from Work/School Related to Adjudicated PEs per Patient Year Over the 52-Week Treatment period

The number of days absent from work/school will be presented and will utilize the ITT Analysis Set (see Section 5.2). The derivation of the endpoint is detailed in Section 6.7.1.5.

The number and percentage of participants missing work/school, including the person-time (follow-up time) and the number of days missed per person-year will be summarized descriptively by treatment group.

# 8.5.5. Change from Baseline in Prebronchodilator and Postbronchodilator FEV1, FVC, PEFR, ppFEV1 and FEF25-75% to Weeks 16, 28, 40, and 52

The change from baseline in prebronchodilator and postbronchodilator FEV1, FVC, PEFR, ppFEV1 and FEF25-75% to Weeks 16, 28, 40, and 52 will be presented based on the ITT Analysis Set. The derivation of the endpoint is detailed in Section 6.7.3.

Assessments including the changes from baseline will be summarized by time point similar to the display of postbronchodilator  $FEV_1$  in Section 8.3.3.1.

To note: postbronchodilator  $FEV_1$  will be evaluated as part of secondary endpoint analysis in Section 8.3.3.1. Outputs will show prebronchodilator for  $FEV_1$  only.

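### The SAP reports follow-up time as the person-time beside hospital-day and absence-day rates that are divided by time on treatment, and it drops hospital stays with no discharge date from the day count

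*SAP*

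**What the plan says.** **Derivation.** SAP 6.7.1.4 gives the hospital-day rate per arm as "total number of days hospitalized due to indication under study by the total time on treatment". SAP 6.7.1.5 says the absence rate "is calculated as total number of days missed by the total time on treatment".

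**Output.** SAP 8.5.3 says "the person-time (follow-up time) and the number of days hospitalized per person-year will be summarized descriptively". SAP 8.5.4 has the parallel wording, "including the person-time (follow-up time) and the number of days missed per person-year". Both sections refer back to 6.7.1.4 and 6.7.1.5 for the derivation.

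**Durations.** SAP 6.4.7 defines follow-up time as end-of-study date minus first IP intake, in years. It has no entry called time on treatment. It offers exposure duration (last minus first IP intake, plus one day) and a treatment duration net of missed doses, whose formula refers to itself.

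**Which days count.** SAP Table 8 assigns both endpoints to the On-IP estimand with "Early discontinuation from randomized IP / While On-Treatment". SAP 6.6 says data collected after stopping IP are reported "per the corresponding estimand, specifically the ICE handling strategy".

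**Missing dates.** SAP 6.7.1.4 says: "For missing admission or discharge dates, the duration of hospitalization will not be calculated". By contrast, SAP 6.7.1 closes a pulmonary exacerbation still ongoing at the end of study at that date once the query has failed, and uses the cut-off date for participants still in the study at the primary analysis.

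**The concern.** A rate table should let the reader divide the displayed days by the displayed person-time and obtain the displayed rate. Here the derivation sections and the output sections name two different periods. The longer one also includes the four weeks after Week 52, when the protocol's schedule of assessments (Table 5) no longer collects health resource use or missed work/school days. The gap widens with early stopping of drug, because participants who stop are asked to remain in the study.

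The missing-date rule matters for another reason. A participant still in hospital when observation ends is the one most likely to have no discharge date, and may have a long stay. Leaving that stay out lowers the numerator while the exposure remains in the divisor.

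At stake are the accuracy and reproducibility of two descriptive tables. SAP 6.7.5.8 also refers to 6.7.1.4 for hospitalizations per person-year, so any ambiguity there carries over to the health-resource summary.

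**Working it through.** The plan states no figure for these rates, so there is none to reproduce. The check compares the two periods.

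**Inputs.** First dose on Day 1, Week 52 visit on Day 364 and end-of-study visit on Day 392 (protocol Table 5). Study drug is given at the Week 52 visit (protocol 5.3), so the scheduled last dose is Day 364. Time on treatment is taken as exposure duration in SAP 6.4.7.

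**Scheduled completer, no assumptions about discontinuation.**
- Time on treatment = 364 − 1 + 1 = 364 days = 0.997 years.
- Follow-up time = 392 − 1 = 391 days = 1.070 years.
- Ratio = 391/364 = 1.074, so the displayed person-time is 7.4% too long for the rate beside it.
- A reader who divides by it gets 364/391 = 0.931 of the reported rate.

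**With early stopping of IP.** The documents give no discontinuation rate. Assume a share d stops at a mean of Day 182.
- Mean time on treatment = 364(1 − d) + 182d.
- If all who stop stay to Week 56, mean follow-up = 391.
- If all who stop leave four weeks later, their follow-up is 182 + 28 − 1 = 209 days, and mean follow-up = 391(1 − d) + 209d.

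| d | Time on treatment (days) | Follow-up / treatment, all stay | Follow-up / treatment, all leave |
|---|---|---|---|
| 10% | 345.8 | 391/345.8 = 1.13 | 372.8/345.8 = 1.08 |
| 20% | 327.6 | 391/327.6 = 1.19 | 354.6/327.6 = 1.08 |
| 30% | 309.4 | 391/309.4 = 1.26 | 336.4/309.4 = 1.09 |

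**Stays with a missing date (hospital days only).** Let H be the true on-drug hospital days, m the share of H in stays with a missing date, and T the time on treatment. The reported rate is H(1 − m)/T against a true H/T, so it is low by the fraction m. With m assumed at 2%, 5% or 10%, the rate is low by 2%, 5% or 10%. Absence days come from a recorded number of days, so this rule does not reach them.

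**The case against.** The best defence is that the planned rates are internally sound. A reader of 6.7.1.4 and 6.7.1.5 alone might infer that days are counted over the whole study and divided by time on drug only, which would inflate the rates and do so unequally if the arms stop drug at different rates. The documents do not support that reading. Table 8 sets a While On-Treatment strategy for both endpoints, and SAP 6.6 makes data after stopping follow that strategy, so the numerator is already limited to on-drug days. The derivation sections only fail to restate the limit.

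Nor does any section divide by follow-up time, so an inference that the rate is too low for that reason also fails. No rate ratio or test is planned for these endpoints, so there is no planned comparison to bias.

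On missing dates, the SAP does not say that such stays are set to zero, and SAP 6.9 places missing-data handling after efforts to obtain the data have failed. Closing an undated stay by rule could also overcount days.

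This defence disposes of the claim that numerator and divisor cover different periods. It does not remove the conflict between divisor and displayed person-time. It also does not change the fact that, in a sum, a stay with no duration adds no days.

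**Conclusion.** The point holds in two limited parts.

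1. **Displayed person-time.** It does not match the divisor. The excess is 7.4% for a scheduled completer, using only the protocol schedule and exposure duration as the divisor. Under the assumed 10% to 30% early stopping at a mean of Day 182, it is about 8% to 26%, depending on how many who stop remain in the study. If the divisor is meant to be net of missed doses, the gap is larger. The fault lies in the displayed person-time, not in the planned rate.
2. **Hospital days.** A stay without a discharge date leaves the numerator but not the denominator. The rate is understated by the share of days in such stays, which the documents do not give.

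Both endpoints are exploratory, summarized descriptively, and outside the twelve hypotheses in the multiplicity procedure. No primary or secondary conclusion depends on this. It is worth correcting because it is cheap, but it is minor.

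**What to change.** 1. **SAP 8.5.3 and 8.5.4.** Replace the follow-up-time label with the same on-IP time used as the divisor. Set that time as exposure duration in 6.4.7 (first to last IP intake), and name it in 6.7.1.4 and 6.7.1.5.
2. **SAP 6.7.1.4, missing discharge.** For a stay with a known admission date and no discharge date after query, close it at the earliest of death, end of study, data cut-off or last IP intake. Report the number of stays closed this way, so that any overcount can be judged.
3. **SAP 6.7.1.4, cut-off.** Restate that stays are truncated at last IP intake.
4. **SAP 6.7.1.5, absence days.** These are recorded as a count since the last visit, so the interval spanning the last dose needs its own rule. Either count days up to the last on-drug visit and divide by time to that visit, or prorate the days in the spanning interval to last IP intake and divide by exposure duration. Cutting days at the last on-drug visit while dividing by time to last intake would create a new mismatch. Show the chosen divisor in 8.5.4.

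The cost is wording in four short SAP sections and a small programming change. The dates needed are already collected, except individual absence dates, which item 4 works around.
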